4.4.2.2. Incident cases

Capture-recapture

Capture-recapture methods will be used for incident cases as they were for prevalent cases in those sites where they can be used. Each source of a case report will be recorded to allow these calculations.

CHARS and the administrative data from the health plans will be used to assess the completeness of case ascertainment from clinical sites. These databases will be accessed annually to obtain counts (plus indirect identifiers) of youth with diabetes; i.e. these numbers would serve as a “denominator” for all potential youth with diabetes. Cases enrolled in SEARCH who have given consent for review of medical records/databases will be matched using these indirect identifiers to those found in the databases.

Random sample of primary care practices

Extensive case identification from a random sample of primary care practice will also be used to estimate the completeness of case ascertainment.

Death certificates

Information from death certificates on individuals with diabetes listed as cause of death will be requested from the state department of Vital Statistics. This information will be matched against local SEARCH database to further assess completeness of case ascertainment. Cases identified using only death certificates will be classified as death-certificate-only cases.

Table V – 1. Estimated Number of Prevalent Cases Type 1 Based on Incidence * Denominator Except for Hawaii

Age	Non-Hispanic White			African American			Hispanic			Asian			Pacific Islander			Native American			ALL
	Rate	Denom	N	Rate	Denom	N	Rate	Denom	N	Rate	Denom	N	Rate	Denom	N	Rate	Denom	N	
0 thru 9																			
California ¹	1	170740	170	1	32621	32	0.5	100294	50	0.1	28997	2	1	7249	7	0.01	1742	0	261
Colorado ²	1	302760	302	1	22787	22	0.5	56145	28	0.1	7558	0	1	1890	1	0.01	64853	0	353
Hawaii ³	1	26295	26	1	3310	3	0.5	13733	6	0.3	50754	15	2	20914	41	0.01	319	0	91
Ohio ⁴	1	235,458	235	1	31,556	31	0.5	0	0	0.1	0	0	1	0	0	0.01	0	0	266
Seattle ⁵	1	383,387	383	1	32446	32	0.5	26367	13	0.1	34422	3	1	8605	8	0.01	7783	0	439
S Carolina ⁶	1	44377	44	1	37798	37	0.5	2319	1	0.1	968	0	1	33	0	0.01	212	0	82
10 thru 19																			
California ¹	2.2	179361	394	2.2	34269	75	1.8	105359	189	0.8	30461	24	2.5	7615	19	0.01	1742	0	701
Colorado ²	2.2	261705	575	2.2	19464	42	1.8	49072	88	0.8	7290	5	2.5	1822	4	0.01	67412	0	714
Hawaii ³	2.2	28486	62	2.2	3585	7	1.8	14877	26	1.6	54984	87	3	22657	67	0.01	346	0	249
Ohio ⁴	2.2	249,921	549	2.2	33,495	73	1.8	0	0	0.8	0	0	2.5	0	0	0.01	0	0	622
Seattle ⁵	2.2	380465	837	2.2	29337	64	1.8	24479	44	0.8	37947	30	2.5	9487	23	0.01	8195	0	998
S Carolina ⁶	2.2	49497	108	2.2	42300	93	1.8	2585	4	0.8	1099	0	2.5	37	0	0.01	299	0	205
Total		2312452	3685		322968	511		395230	449		254480	166		80309	170		152903	0	4981

Table V – 2. Estimated Number of Prevalent Cases Type 2 Based on Incidence * Denominator Except for Hawaii

Age	Non-Hispanic White			African American			Hispanic			Asian			Pacific Islander			Native American			ALL
	Rate	Denom	N	Rate	Denom	N	Rate	Denom	N	Rate	Denom	N	Rate	Denom	N	Rate	Denom	N	
0 thru 9																			
California ¹	0.05	170740	8	0.05	32621	1	0.13	100294	13	0.1	28997	2	0.11	7249	0	0.4	1742	0	24
Colorado ²	0.05	302760	15	0.05	22787	1	0.13	56145	7	0.1	7558	0	0.11	1890	0	0.4	64853	25	48
Hawaii ³	0.05	26295	1	0.05	3310	0	0.13	13733	1	0.2	50754	10	0.2	20914	4	0.4	319	0	16
Ohio ⁴	0.05	235,458	11	0.05	31,556	1	0.13	0	0	0.1	0	0	0.11	0	0	0.4	0	0	12
Seattle ⁵	0.05	383,387	19	0.05	32446	1	0.13	26367	3	0.1	34422	3	0.11	8605	0	0.4	7783	3	29
S Carolina ⁶	0.05	44377	2	0.05	37798	1	0.13	2319	0	0.1	968	0	0.11	33	0	0.4	212	0	3
10 thru 19																			
California ¹	0.39	179361	69	1.18	34269	40	1.46	105359	153	0.78	30461	23	1.07	7615	8	1.7	1742	2	295
Colorado ²	0.39	261705	102	1.18	19464	22	1.46	49072	71	0.78	7290	5	1.07	1822	1	1.7	67412	114	315
Hawaii ³	0.39	28486	11	1.18	3585	4	1.46	14877	21	1.8	54984	98	2	22657	45	1.7	346	0	179
Ohio ⁴	0.39	249,921	97	1.18	33,495	39	1.46	0	0	0.78	0	0	1.07	0	0	1.7	0	0	136
Seattle ⁵	0.39	380465	148	1.18	29337	34	1.46	24479	35	0.78	37947	29	1.07	9487	10	1.7	8195	13	269
S Carolina ⁶	0.39	49497	19	1.18	42300	49	1.46	2585	3	0.78	1099	0	1.07	37	0	1.7	299	0	71
Total		2312452	502		7	193		395230	307		254480	170		80309	68		152903	157	1397

TOTALS		
Estimated Prevalent Cases		
	TOTAL	
California ¹	1281	Rates are per 1,000
Colorado ²	1430	¹ California (KPSC) - all but SD
Hawaii ³	535	² Colorado - urban Denver counties, other selected CO counties, Pima, Apache, and Navaho in Arizona, NM
Ohio ⁴	1036	³ Hawaii - members of 3 major health plans residing on Oahu
Seattle ⁵	1735	⁴ Ohio (Cincinnati) - Cincinnati and 8 urban counties
S Carolina ⁶	361	⁵ Seattle - 5 counties
	6378	⁶ S Carolina - 4 counties

Table V – 3. Estimated Number of Prevalent Cases All Types Based on Incidence Plus Denominator Except for Hawaii

	Non-Hispanic White			African American			Hispanic			Asian			Pacific Islander			Native American			ALL
Age	Rate	Denom	N	Rate	Denom	N	Rate	Denom	N	Rate	Denom	N	Rate	Denom	N	Rate	Denom	N	
0 thru 9																			
California ¹	1	170740	178	1	32621	33	0.5	100294	63	0.1	28997	4	1	7249	7	0.01	1742	0	285
Colorado ²	1	302760	317	1	22787	23	0.5	56145	35	0.1	7558	0	1	1890	1	0.01	64853	25	401
Hawaii ³	1	26295	27	1	3310	3	0.5	13733	7	0.3	50754	25	2	20914	45	0.01	319	0	107
Ohio ⁴	1	235,458	246	1	31,556	32	0.5	0	0	0.1	0	0	1	0	0	0.01	0	0	278
Seattle ⁵	1	383,387	402	1	32446	33	0.5	26367	16	0.1	34422	6	1	8605	8	0.01	7783	3	468
S Carolina ⁶	1	44377	46	1	37798	38	0.5	2319	1	0.1	968	0	1	33	0	0.01	212	0	85
10 thru 19																			
California ¹	2.2	179361	463	2.2	34269	115	1.8	105359	342	0.8	30461	47	2.5	7615	27	0.01	1742	2	996
Colorado ²	2.2	261705	677	2.2	19464	64	1.8	49072	159	0.8	7290	10	2.5	1822	5	0.01	67412	114	1029
Hawaii ³	2.2	28486	73	2.2	3585	11	1.8	14877	47	1.6	54984	185	3	22657	112	0.01	346	0	428
Ohio ⁴	2.2	249,921	646	2.2	33,495	112	1.8	0	0	0.8	0	0	2.5	0	0	0.01	0	0	758
Seattle ⁵	2.2	380465	985	2.2	29337	98	1.8	24479	79	0.8	37947	59	2.5	9487	33	0.01	8195	13	1267
S Carolina ⁶	2.2	49497	127	2.2	42300	142	1.8	2585	7	0.8	1099	0	2.5	37	0	0.01	299	0	276
Total		2312452	4187		322968	704		395230	756		254480	336		80309	238		152903	157	6378

Table V – 4. Estimated Annual Number of Incident Cases Type 1

Age	Non-Hispanic White			African American			Hispanic			Asian			Pacific Islander			Native American			ALL
	Rate	Denom	N	Rate	Denom	N	Rate	Denom	N	Rate	Denom	N	Rate	Denom	N	Rate	Denom	N	
0 thru 9																			
California	13.5	170740	23	9.5	32621	3	7	100294	7	0.9	28997	0	12.7	7249	0	0	1742	0	33
Colorado	13.5	504413	68	9.5	32685	3	7	121224	8	0.9	14948	0	12.7	725	0	0	74453	0	79
Hawaii	13.5	32869	4	9.5	4137	0	7	17166	1	4	63443	2	15	26143	3	0	399	0	10
Ohio	13.5	235,458	31	9.5	31,556	2	7	0	0	0.9	0	0	12.7	0	0	0	0	0	33
Seattle	13.5	383,387	51	9.5	32446	3	7	26367	1	0.9	34422	0	12.7	8605	1	0	7783	0	56
S Carolina	13.5	319645	43	9.5	195522	18	7	17146	1	0.9	4727	0	12.7	173	0	0	1833	0	62
10 thru 19																			
California	16.7	179361	29	13.1	34269	4	11.4	105359	12	3.2	30461	0	14	7615	1	0	1742	0	46
Colorado	16.7	451376	75	13.1	27703	3	11.4	102736	11	3.2	13234	0	14	642	0	0	76700	0	89
Hawaii	16.7	35608	5	13.1	4482	0	11.4	18596	2	4	68730	2	16	28321	4	0	433	0	13
Ohio	16.7	249,921	41	13.1	33,495	4	11.4	0	0	3.2	0	0	14	0	0	0	0	0	45
Seattle	16.7	380465	63	13.1	29337	3	11.4	24479	2	3.2	37947	1	14	9487	1	0	8195	0	70
S Carolina	16.7	341223	56	13.1	214334	28	11.4	16134	1	3.2	4966	0	14	202	0	0	2117	0	85
Total		3284466	489		672587	71		549501	46		301875	5		89162	10		175397	0	621

Table V – 5. Estimated Annual Number of Incident Cases Type 2

Age	Non-Hispanic White			African American			Hispanic			Asian			Pacific Islander			Native American			ALL
	Rate	Denom	N	Rate	Denom	N	Rate	Denom	N	Rate	Denom	N	Rate	Denom	N	Rate	Denom	N	
0 thru 9																			
California	0.7	170740	1	5	32621	1	1.8	100294	1	2.07	28997	0	3.3	7249	0	4.7	1742	0	3
Colorado	0.7	504413	3	5	32685	1	1.8	121224	2	2.07	14948	0	3.3	725	0	4.7	74453	3	9
Hawaii	0.7	32869	0	5	4137	0	1.8	17166	0	2.07	63443	1	5	26143	1	4.7	399	0	2
Ohio	0.7	235,458	1	5	31,556	1	1.8	0	0	2.07	0	0	3.3	0	0	4.7	0	0	2
Seattle	0.7	383,387	2	5	32446	1	1.8	26367	0	2.07	34422	0	3.3	8605	0	4.7	7783	0	3
S Carolina	0.7	319645	2	5	195522	9	1.8	17146	0	2.07	4727	0	3.3	173	0	4.7	1833	0	11
10 thru 19																			
California	2.9	179361	5	7.2	34269	2	9.5	105359	10	13.9	30461	4	11.3	7615	0	21.3	1742	0	21
Colorado	2.9	451376	13	7.2	27703	1	9.5	102736	9	13.9	13234	1	11.3	642	0	21.3	76700	16	40
Hawaii	2.9	35608	1	7.2	4482	0	9.5	18596	1	13.9	68730	9	22	28321	6	21.3	433	0	17
Ohio	2.9	249,921	7	7.2	33,495	2	9.5	0	0	13.9	0	0	11.3	0	0	21.3	0	0	9
Seattle	2.9	380465	11	7.2	29337	2	9.5	24479	2	13.9	37947	5	11.3	9487	1	21.3	8195	1	22
S Carolina	2.9	341223	9	7.2	214334	15	9.5	16134	1	13.9	4966	0	11.3	202	0	21.3	2117	0	25
Total		3284466	55		672587	35		549501	26		301875	20		89162	8		175397	20	164

Estimated Incident Cases	
	TOTAL
California	103
Colorado	217
Hawaii	42
Ohio	89
Seattle	151
S Carolina	183
	785
Rates are per 100,000	

Table V – 6. Estimated Annual Number of Incident Cases All Types

Age	Non-Hispanic White			African American			Hispanic			Asian			Pacific Islander			Native American			ALL
	Rate	Denom	N	Rate	Denom	N	Rate	Denom	N	Rate	Denom	N	Rate	Denom	N	Rate	Denom	N	
0 thru 9																			
California	0.7	170740	24	5	32621	4	1.8	100294	8	2.07	28997	0	3.3	7249	0	4.7	1742	0	36
Colorado	0.7	504413	71	5	32685	4	1.8	121224	10	2.07	14948	0	3.3	725	0	4.7	74453	3	88
Hawaii	0.7	32869	4	5	4137	0	1.8	17166	1	2.07	63443	3	5	26143	4	4.7	399	0	12
Ohio	0.7	235,458	32	5	31,556	3	1.8	0	0	2.07	0	0	3.3	0	0	4.7	0	0	35
Seattle	0.7	383,387	53	5	32446	4	1.8	26367	1	2.07	34422	0	3.3	8605	1	4.7	7783	0	59
S Carolina	0.7	319645	45	5	195522	27	1.8	17146	1	2.07	4727	0	3.3	173	0	4.7	1833	0	73
10 thru 19																			
California	2.9	179361	34	7.2	34269	6	9.5	105359	22	13.9	30461	4	11.3	7615	1	21.3	1742	0	67
Colorado	2.9	451376	88	7.2	27703	4	9.5	102736	20	13.9	13234	1	11.3	642	0	21.3	76700	16	129
Hawaii	2.9	35608	6	7.2	4482	0	9.5	18596	3	13.9	68730	11	22	28321	10	21.3	433	0	30
Ohio	2.9	249,921	48	7.2	33,495	6	9.5	0	0	13.9	0	0	11.3	0	0	21.3	0	0	54
Seattle	2.9	380465	74	7.2	29337	5	9.5	24479	4	13.9	37947	6	11.3	9487	2	21.3	8195	1	92
S Carolina	2.9	341223	65	7.2	214334	43	9.5	16134	2	13.9	4966	0	11.3	202	0	21.3	2117	0	110
Total		3284466	544		672587	106		549501	72		301875	25		89162	18		175397	20	785

Table V - 7. Prevalence (per 1000) of Diabetes by Age, Type and Ethnicity: Rates Based on the Published Literature and Unpublished Data Available to SEARCH Investigators

	NHW	AA	Asian	PI	NA	Hispanic
Type 1						
Age 0-9	1.00	1.00	0.10	1.00	0.01	0.50
Age 10-19	2.20	2.20	0.80	2.50	0.01	1.80
Type 2						
Age 0-9	0.05	0.05	0.10	0.11	0.40	0.13
Age 10-19	0.39	1.18	0.78	1.07	1.70	1.46

NHW = non-Hispanic white, AA = African American, PI = Pacific Islander, NA = Native American

Table V – 8. Estimated Incidence (per 100,000 per year) of Diabetes by Age, Type and Ethnicity: Rates Based on the Published Literature and Unpublished Data Available to SEARCH Investigators

	NHW	AA	Asian	PI	NA	Hispanic
Type 1						
Age 0-9	13.5 ^a	9.5 ^c	0.9 ^h	12.7 ^j	0	7.0 ^a
Age 10-19	16.7 ^a	13.1 ^d	3.2 ^h	14.0 ^j	0	11.4 ^a
Type 2						
Age 0-9	0.7 ^b	5.0 ^c	2.07 ⁱ	3.3 ^k	4.7 ^g	1.8 ^b
Age 10-19	2.9 ^b	7.2 ^f	13.9 ⁱ	11.3 ^k	21.3 ^g	9.5 ^b

NHW = non-Hispanic white, AA = African American, PI = Pacific Islander, NA = Native American

^a using 1978-1988 Colorado incidence rates

^b estimated from ^a using type1/type 2 prevalence rates

^c estimated based on data from Libman et al. Diabetes Care 21:1278, 1998

^d estimated from ^f using type1/type2 prevalence rates

^e using S. Carolina Pilot registry data supplied by [name]

^f using data from Pinhas-Hamiel et al. J Pediatr 128: 608, 1996

^g using Pima Indian data from NIDDK, [name]

^h averaged using data from Asians in Hawaii (Patrick et al. Diabetes Care 20: 983, 1997) and from China and Japan (Karvonen et al. Diabetes Care 23:1516, 2000)

^l using data from Kitagawa et al. Diabetes Res Clin Pract 24 (Suppl.): S7, 1994 and Clin Pediatr 37: 111, 1998

^j estimated from Karvonen et al. Diabetes Care 23:1516, 2000

^k estimated from ^j using type1/type 2 prevalence rates

* Rates for Asians and Pacific Islanders in Hawaii are based on unpublished actual counts of cases of diabetes available in Hawaii

Table V - 9. Estimated Prevalence Denominators by Center, Age Group, and Ethnicity^a

Estimated Number of Prevalent Cases Type 1							
Age	NHW	AA	Hispanic	Asian	PI	Nat.Am.	Total
0 thru 9							
California	170740	32621	100294	28997	7249	1742	341,643
Colorado	302760	22787	56145	7558	1890	64853	455,993
Hawaii	26295	3310	13733	50754	20914	319	115,325
Ohio	235,458	31,556	0	0	0	0	267,014
Seattle	383,387	32446	26367	34422	8605	7783	493,010
S Carolina	44377	37798	2319	968	33	212	85,707
10 thru 19							
California	179361	34269	105359	30461	7615	1742	358,807
Colorado	261705	19464	49072	7290	1822	67412	406,765
Hawaii	28486	3585	14877	54984	22657	346	124,935
Ohio	249,921	33,495	0	0	0	0	283,416
Seattle	380465	29337	24479	37947	9487	8195	489,910
S Carolina	49497	42300	2585	1099	37	299	95,817

^a Incidence denominators are estimated from the 2000 census for geographic-based centers (Cincinnati, Colorado, Seattle, S. Carolina, and from 2000 membership data for member-based centers (Hawaii and S. California. NHW = non-Hispanic white, AA = African American, PI = Pacific Islander, NA = Native American

* Totals do not add due to rounding

Table V - 10. Estimated Incidence Denominators by Center, Age Group, and Race/Ethnicity^a

Age	NHW	AA	Hispanic	Asian	PI	NA	Total
0 thru 9							
California	170740	32621	100294	28997	7249	1742	341,643
Colorado	504413	32685	121224	14948	725	74453	748,448
Hawaii	32869	4137	17166	63443	26143	399	144,157
Ohio	235,458	31,556	0	0	0	0	267,014
Seattle	383,387	32446	26367	34422	8605	7783	493,010
S Carolina	319645	195522	17146	4727	173	1833	539,046
10 thru 19							
California	179361	34269	105359	30461	7615	1742	358,807
Colorado	451376	27703	102736	13234	642	76700	672,391
Hawaii	35608	4482	18596	68730	28321	433	156,170
Ohio	249,921	33,495	0	0	0	0	283,416
Seattle	380465	29337	24479	37947	9487	8195	489,910
S Carolina	341223	214334	16134	4966	202	2117	578,976
Total	3284466	672587	549501	301875	89162	175397	5,072,988

^a Incidence denominators are estimated from the 2000 census for geographic-based centers (Cincinnati, Colorado, Seattle, S. Carolina, and from 2000 membership data for member-based centers (Hawaii and S. California. NHW = non-Hispanic white, AA = African American, PI = Pacific Islander, NA = Native American

* Totals do not add due to rounding

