4.3.1. Capture-Recapture

Capture-recapture²⁸⁻³¹ is a statistical approach that attempts to estimate the completeness from incomplete samples. This method requires a minimum of two data sources in which a case can be identified. The data elements that are required to derive estimates of the completeness of case ascertainment using capture-recapture methods are 1) the source(s) of the case record for each unique case identified and 2) the date of inclusion in the data source. Records must be non-duplicates. These data elements will be collected in SEARCH from unduplicated records. The best statistical methods will be used, incorporating multiple ascertainment sources, with adjustment for non-independence of data sources. Capture-recapture methods will be used in the geographically-based SEARCH centers with multiple sources of cases (Cincinnati, Colorado, Seattle, South Carolina).

4.3.2. **Intensive Case-Finding**

Another way to estimate the completeness of case ascertainment is to conduct extended, intensive case-finding of all available potential sources of cases, or to identify multiple independent computerized databases. While possible, limited resources preclude complete review of all records in defined geographic areas with multiple providers that do not share common information systems.

At the Seattle, South Carolina, and Colorado centers, intensive case-finding will be done based on a mailed survey to a defined sample of providers in specialties likely to see youth with diabetes who are not included in primary case ascertainment. Such specialties include: pediatrics, family medicine, general internal medicine, adolescent medicine, and adult endocrinology. Other specialties such as OB/GYN, school-based clinics, emergency medicine, alternative providers, and PAs or NPs who work with providers previously listed will be considered for survey to establish practice and referral patterns for youth with diabetes in these geographic areas.

A random sample of providers who indicate that they care for children with diabetes will be asked to review their clinical and billing databases and/or chart review to find cases of diabetes in children. These cases will be compared with cases that have already been identified by SEARCH as permitted by local IRBs.

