5.4. CASE REGISTRATION MODULE (INCIDENT AND PREVALENT CASES)

Eligible Patients: Incident and Prevalent Cases

Case Registration closes the gap between case ascertainment, which is a local effort and data collection, which is a national effort. Case Registration occurs when a unique (unduplicated) case is validated and age and residence eligibility are established. The process of case registration initiates all other data collection. Information gathered at the time of case registration is minimal. Depending on the local case ascertainment approach, some data elements requested for case registration may be missing at the time of registration and will be completed or verified within a later data collection module (e.g., Initial Patient Survey). At some centers, Case Registration will occur based on anonymous case reports collected by the local center. For all centers, when identifying information becomes available, it will remain at the local center and will not be forwarded to the Coordinating Center.

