If the hospitals are unwilling to share direct identifiers (e.g. name, SSN, parental contact information), indirect identifiers (e.g. date of birth, gender, residential zipcode, date of diagnosis) will be used to assess completeness of case ascertainment from the clinical non-hospital based sites.

d) Primary care clinics

Primary care practices found to care for youth with diabetes independently of endocrinologists will be included in the surveillance network for incident case ascertainment.

A targeted effort to find cases may involve direct contact with practices in more rural areas (farther away from referral centers) and practices serving geographic areas where more ethnic minorities live (populations at greater risk for type 2).

e) Community Diabetes Registry

Refer to section 4.2.1.1(e) for discussion on DEMS and the CDI. Medical directors in the CDI network will be approached for permission to be a source for incident cases.

f) Group Health Diabetes Registry

Refer to section 4.2.1.1 (f) for discussion on the Group Health diabetes registry. This registry is updated daily and will be used to identify incident cases. The registry will be queried monthly for new cases. Primary care providers for these cases will be contacted to determine if they are new diagnoses or new enrollees with diabetes and to establish case validation.

Additional sources

Additional data sources considered to identify incident cases include:

- Certified Diabetes Educators
- School nurses

Working relationships with these groups are currently being explored.

Case definition and eligibility

Incident diagnosis years will begin in 2002 and continue for the period of the project. Cases are eligible to be counted as incident when diagnosed from January 1 through December 31 of that year.

- a) “Onset of diabetes” is the date of first clinical diagnosis of diabetes in a non-pregnant state.
- b) Age range: 0 – 19.999 in the onset year
- c) Resident of population defined for incident cases: 5-county Puget Sound Region, Washington (King, Kitsap, Pierce, Snohomish and Thurston Counties).

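### Seattle's supplementary incident completeness check matches only consenting enrolled cases against database counts that carry no consent limit, so it understates completeness

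*Protocol*

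**What the plan says.** The passage is the second paragraph under capture-recapture in section 4.4.2.2 of the Puget Sound site protocol. Its purpose is stated first: "CHARS and the administrative data from the health plans will be used to assess the completeness of case ascertainment from clinical sites". The comparison set follows: "These databases will be accessed annually to obtain counts (plus indirect identifiers) of youth with diabetes", and "these numbers would serve as a “denominator” for all potential youth with diabetes". No consent condition is attached to these counts. The next sentence limits who can be matched: "Cases enrolled in SEARCH who have given consent for review of medical records/databases will be matched using these indirect identifiers".

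Elsewhere the protocol counts a case as found before any such consent. Section 5.4 says "Case Registration occurs when a unique (unduplicated) case is validated and age and residence eligibility are established", and adds that "At some centers, Case Registration will occur based on anonymous case reports collected by the local center". Section 11.6 lists case registration and the medical record module as separate, voluntary levels of involvement. Seattle's section 4.4.1 speaks of cases consenting to medical record review, so consent is not taken to be universal.

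The core capture-recapture text (section 4.3.1) asks for "the source(s) of the case record for each unique case identified". Seattle's own section 4.3.3.1 provides that, if hospitals withhold direct identifiers, indirect ones "will be used to assess completeness of case ascertainment from the clinical non-hospital based sites", with no consent limit. The death-certificate check in section 4.4.2.2 is run against the local SEARCH database, also without one.

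**The concern.** The two sides of the comparison are on different bases. The database count includes youth whether or not they agreed to record review. The matched set includes only those who were enrolled and agreed. Non-consenters, non-responders and cases never reached for consent can all be registered and validated, yet none can be matched. The paragraph has no category for registered cases without consent and no correction for them.

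Section 4.3 calls the assessment of completeness crucial to the study's objectives. A check that mixes refusal with failure to find cases cannot tell a reader which one occurred. If consent differs by age, race/ethnicity or diabetes type, an apparent gap in ascertainment between those groups could be a gap in consent.

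**Working it through.** The protocol states no completeness figure, so there is none to reproduce. For scale I use Seattle's expected 151 incident cases a year (Table 3-2; 59 aged 0-9 plus 92 aged 10-19 in Table 4-3). Summing rate × denominator over the Seattle cells of Tables V-4 and V-5, with each cell cut to a whole number, gives 151. Unrounded, the sum is 160.5.

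**Inputs**
- N = 151, the true number of incident cases, for illustration.
- C = true completeness of registration. Not stated; 95% assumed, with 100% as a limiting case.
- c = share of registered cases enrolled and consenting to record/database review. Not stated for Seattle. I use 90%, 75% and 50%. Section 8.2 assumes 75% participation study-wide for the power table; it is a reference point only.
- h = share of true cases listed in the databases. Not stated; 70% used as an example.
- Consent and registration are taken as unrelated to database listing, and the database list is taken to hold only eligible incident cases.

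**The ratio as described**

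Database list = N × h. Matches = N × h × C × c. Ratio = (N × h × C × c) / (N × h) = C × c.

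| c | Ratio if C = 95% | Ratio if C = 100% |
|---|---|---|
| 90% | 0.95 × 0.90 = 85.5% | 90% |
| 75% | 0.95 × 0.75 = 71.3% | 75% |
| 50% | 0.95 × 0.50 = 47.5% | 50% |

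Coverage cancels. With h = 70%, the list is 151 × 0.70 = 105.7, matches are 105.7 × 0.7125 = 75.3, and the ratio is again 71.3%.

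Read across 151 cases with C = 95% and c = 75%, about 151 × (1 − 0.7125) = 43 would appear missed, against 151 × 0.05 = 8 truly missed.

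**Both sides on the same basis**

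- All registered cases matched: ratio = (N × h × C) / (N × h) = C, which is 95% in the example.
- Both sides limited to consenters, with h = 70%: consenters = 151 × 0.95 × 0.75 = 107.6 and matched consenters = 75.3. Coverage = 75.3 / 107.6 = 0.70. Estimated total = 105.7 / 0.70 = 151. Registered cases = 151 × 0.95 = 143.5, and 143.5 / 151 = 95%.

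Either route removes the bias. The paragraph specifies neither.

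**The case against.** The strongest reply is that this is only a supplementary check. The first paragraph of the same section plans capture-recapture for incident cases as for prevalent ones and has every case-report source recorded, with no consent limit. That stands: Seattle has not replaced the core method, and the source-based estimate is untouched.

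A second reply is that no estimator is written down, so matched consenters over all consenters might be intended. This stands only in part. The text calls the database counts the denominator, which makes the ratio above the natural reading, and nothing limits the other side.

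A third is that the consent limit may be needed for access to protected records (sections 4.1 and 11.5; section 4.3.2 makes case comparison subject to local IRBs). That may explain the restriction, but it does not make the resulting ratio a measure of completeness.

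A fourth is that C × c assumes a clean list of incident cases. Seattle's section 4.3.1.1(h) says the annual plan tapes make identifying incident cases infeasible, so plan counts may include prevalent youth. This stands: it is a separate reason the ratio could be low, and matching every registered case would not cure it alone.

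Stronger readings are tempting but unsupported:
- A reader might infer an inflated incidence rate. At 75% consent, a two-list estimate with all registered cases as the first list but matches among consenters only would give 151 / 0.75 = 201 cases. The paragraph does not describe that pairing. Section 8.1.1 says completeness will be assessed, and no section says rates will be corrected by this check.
- A reader might infer that every refusal or withdrawal counts as a missed case. Only non-consenters who appear in a database can look missed, and the paragraph does not mention withdrawal.
- A reader might take the databases to list every youth with diabetes. CHARS holds hospital records, and the plan data come from four named sources.

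**Conclusion.** The concern holds for this one check. As written, it sets a consent-limited match against a count with no consent limit and returns about C × c instead of C. The direction is clear whenever consent is incomplete; the size is not known from the documents. With true completeness of 95%, the reported figure would be about 86% at 90% consent and 71% at 75%. These values rest on assumed C and c, on consent being unrelated to database listing, and on a list of eligible incident cases. False matches on indirect identifiers could push the other way. The consequence is a misleading completeness figure for Seattle's incident cases, and possibly misleading differences between subgroups. It should be corrected before that figure is reported.

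**What to change.** Reword the paragraph so that both sides share one consent basis, and state the estimator.

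- **Where the IRB permits:** match all registered incident cases, whatever their level of participation, on the indirect identifiers that each database actually holds. Date of birth, gender, ZIP code and date of diagnosis are Case Registration items (Table 5-1), although section 5.4 allows some to be missing at first. The plan claims fields in section 4.3.1.1(h) include no date of diagnosis, so use service or admission dates, or diagnosis codes, there. Restrict the database list to eligible, newly diagnosed youth as far as possible.
- **Where consent is required:** estimate database coverage as matched consenters / all consenters, divide the database count of eligible incident youth by that coverage to obtain the total, and compare all registered cases with it. Do not report matched consenters / all database youth as completeness.

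The first option costs a change of site-protocol wording and local IRB confirmation. The second is an analysis change that needs no new data and no change in consent. Its downside is the assumption that consent is unrelated to being listed in a database. It also still depends on separating incident from prevalent youth in the database count.
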